7.4 Clinical Laboratory Tests (Serum Chemistry, Hematology, Coagulation and Urinalysis)

Safety serum chemistry, hematology and urinalysis tests are performed at Screening, Day -8 check-in, and end of HD on Day 3. For anuric patients, urinalysis may not be performed. Coagulation is collected at Screening, Day -8 check-in, start and end of

HD on Days -7, -5, -2, 1, and 3, and at Follow-up. Platelet count is collected at start and end of HD on Days -7, -5, -2, 1, and 3.

Out-of-range values and clinically significant results will be listed.

For serum chemistry and hematology laboratory values, descriptive statistics will be presented for each laboratory test by assessment time point and treatment. Change from baseline will be summarized in a similar manner. Baseline is defined as the result closest and prior to dose which may include unscheduled results. This will typically be the result collected at Day -8 check-in. Postdose unscheduled events or early termination results will not be included in summaries.

For each serum chemistry and hematology laboratory test, a shift table will be developed to compare the frequency of the results at baseline (above normal, normal, or below normal) with the respective postdose results.

For coagulation tests (aPTT, PT/INR, fibrinogen, and TT) and platelet count on HD days, summary will be for pre- and post-HD and fold change. Coagulation parameters and platelet count will be listed and presented together since they have the same timepoints. Urinalysis test results will be listed only.

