14.3.1 Safety and Tolerability Analyses

All safety data will be populated in the individual CRFs. All safety data will be listed by patients.

The placebo patients from all cohorts will be pooled into a single placebo group for all summaries and presentations.

Dosing dates and times will be listed by patient.

Incidence and time of bleeding from the HD access sites on the AV fistula (or AV graft), as described in [Section 13.2.6](#), will be counted and recorded. Active treatment versus pre-treatment, placebo, and post-treatment results will be compared.

AEs will be coded using the most current version of Medical Dictionary for Regulatory Activities (MedDRA®) available at Celerion and summarized by treatment (2 active dose levels and pooled placebo) for the number of patients reporting the treatment emergent adverse event (TEAE) and the number of TEAEs reported. A by-patient AE data listing including verbatim term, coded term, treatment, severity, and relationship to study drug will be provided.

Safety data including ECGs, vital signs assessments, clinical laboratory results, and vascular access site reaction will be summarized by treatment (2 active dose levels and pooled placebo) and point of time of collection.

Descriptive statistics using appropriate summary statistics will be calculated for quantitative safety data as well as for the difference to baseline, when appropriate. In addition, a shift table describing out of normal range shifts will be provided for clinical laboratory results.

Concomitant medications will be listed by patient and treatment (2 active dose levels and pooled placebo) and coded using the most current version of the World Health Organization drug dictionary available at Celerion. Medical history will be listed by patient.

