14.3.3 Pharmacodynamic Analyses

Placebo patients from Cohort 1 and Cohort 2 will be pooled for analysis.

Individual, mean, and median data for APC-PCI will be presented graphically for all treatments (2 active dose levels and pooled placebo).

Analysis will include assessments of drug efficacy and efficiency of HD. These will include changes in thrombus accumulation and measurement of urea removed by 4 hours of dialysis (Kt/V and URR).

The change from baseline in endpoints will be summarized by treatment (2 active dose levels and pooled placebo) and at each scheduled time point using descriptive statistics. The baseline values are any value observed from Day -8 to Day 1, prior to E-WE thrombin administration. An average of predose values may be used as baseline, as applicable. Any values after a single dose of E-WE thrombin are regarded as post-baseline values.

The change from baseline variables will be calculated as the post-baseline value minus the value at baseline.

Additional analyses may be performed as deemed necessary upon review of the data.

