14.3.3 Narratives of Deaths, other Serious and Certain other Significant Adverse Events

14.3.4 Abnormal Laboratory Value Listing (each patient)

Table 14.3.4.1 Out-of-Range Values and Recheck Results – Serum Chemistry (Safety Population)

Table 14.3.4.2 Out-of-Range Values and Recheck Results – Hematology/Coagulation (Safety Population)

Table 14.3.4.3 Out-of-Range Values and Recheck Results – Urinalysis (Safety Population)

14.3.5 Displays of Other Laboratory, Vital Signs, Electrocardiogram, Physical Examination, and Other Safety Data

Table 14.3.5.1 Clinical Laboratory Summary and Change from Baseline – Serum Chemistry (Safety Population)

Table 14.3.5.2 Clinical Laboratory Shift from Baseline – Serum Chemistry (Safety Population)

Table 14.3.5.3 Clinical Laboratory Summary and Change from Baseline – Hematology (Safety Population)

Table 14.3.5.4 Clinical Laboratory Shift from Baseline – Hematology (Safety Population)

Table 14.3.5.5 Clinical Laboratory Summary and Change from Baseline – Coagulation and Platelet Count (Safety Population)

Table 14.3.5.6 Vital Sign Summary and Change from Baseline (Safety Population)

Table 14.3.5.7 Summarization of Weight (Safety Population)

Table 14.3.5.8 12-Lead Electrocardiogram Summary and Change from Baseline (Safety Population)

Table 14.3.5.9 Summarization of Bleeding Time (Safety Population)

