			Mean	X.XX	X.XX	X.XX	X.XX	X.XX	X.XX	X.XX	X.XX	X.XX
			SD	X.XXX	X.XXX	X.XXX	X.XXX	X.XXX	X.XXX	X.XXX	X.XXX	X.XXX
			Minimum	X.XX	X.XX	X.XX	X.XX	X.XX	X.XX	X.XX	X.XX	X.XX
			Median	X.X	X.X	X.X	X.X	X.X	X.X	X.X	X.X	X.X
			Maximum	XX.X	XX.X	XX.X	XX.X	XX.X	XX.X	XX.X	XX.X	XX.X

<include all remaining HD days>

Programmer note: This table will include aPTT, PT, INR, PT/INR, fibrinogen, TT from coagulation and platelet count from hematology. for PT, INR and PT/INR, the pre-dialysis value will be the baseline value for that day and the "change from baseline" will be the fold change from baseline "ie. Post-dialysis / Pre-dialysis.

Note: # = Lowest of the lower ranges and highest of the higher ranges are used. Refer to Appendix 16.1.10.1 for the breakdown.
 Fold change = Post-dialysis / Pre-dialysis

Program: /AAXXXX/ECR/sas_prg/stsas/tab_PROGRAMNAME.sas DDMMYYYY HH:MM

Table 14.3.5.6 Vital Sign Summary and Change from Baseline(Safety Population)

Vital Sign(unit)	Time Point	Statistic	Dose Level of E-WE Thrombin			Change from Baseline*		
			1.5 µg/kg	3.0 µg/kg	Placebo (Pooled)	1.5 µg/kg	3.0 µg/kg	Placebo (Pooled)
XXXXXXXXXX (unit)	Screen	n	XX	XX	XX			
		Mean	X.XX	X.XX	X.XX			
		SD	X.XXX	X.XXX	X.XXX			
		Minimum	X.XX	X.XX	X.XX			
		Median	X.X	X.X	X.X			
		Maximum	XX.X	XX.X	XX.X			
<Also include Days -8, -7, -5 and -2>								
Baseline*		n	XX	XX	XX			
		Mean	X.XX	X.XX	X.XX			
		SD	X.XXX	X.XXX	X.XXX			
		Minimum	X.XX	X.XX	X.XX			
		Median	X.X	X.X	X.X			
		Maximum	XX.X	XX.X	XX.X			
Day X, Hour X.XX		n	XX	XX	XX	XX	XX	XX
		Mean	X.XX	X.XX	X.XX	X.XX	X.XX	X.XX
		SD	X.XXX	X.XXX	X.XXX	X.XXX	X.XXX	X.XXX
		Minimum	X.XX	X.XX	X.XX	X.XX	X.XX	X.XX
		Median	X.X	X.X	X.X	X.X	X.X	X.X
		Maximum	XX.X	XX.X	XX.X	XX.X	XX.X	XX.X

Note: * Baseline is defined as the result closest and prior to the dose on Day 1.

Program: /AXXXXXX/ECR/sas_prg/stsas/tbl PROGRAMNAME.sas DDMMYYYY HH:MM

Table 14.3.5.7 Summarization of Weight (Safety Population)

Time Point	Statistic	Dose Level of E-WE Thrombin		
		1.5 µg/kg	3.0 µg/kg	Placebo (Pooled)
Screen	n	XX	XX	XX
	Mean	X.XX	X.XX	X.XX
	SD	X.XXX	X.XXX	X.XXX
	Minimum	X.XX	X.XX	X.XX
	Median	X.X	X.X	X.X
	Maximum	XX.X	XX.X	XX.X
Day -8, Check-in	n	XX	XX	XX
	Mean	X.XX	X.XX	X.XX
	SD	X.XXX	X.XXX	X.XXX
	Minimum	X.XX	X.XX	X.XX
	Median	X.X	X.X	X.X
	Maximum	XX.X	XX.X	XX.X
Day -7, Before HD	n	XX	XX	XX
	Mean	X.XX	X.XX	X.XX
	SD	X.XXX	X.XXX	X.XXX
	Minimum	X.XX	X.XX	X.XX
	Median	X.X	X.X	X.X
	Maximum	XX.X	XX.X	XX.X

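### For aPTT, PT/INR, fibrinogen and TT, the only planned within-patient change is a same-day ratio, and on Day 3 its denominator is a post-dose sample

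*SAP*

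**What the plan says.** SAP 7.4 schedules coagulation tests at Screening, at Day -8 check-in, at the start and end of "HD on Days -7, -5, -2, 1, and 3, and at Follow-up". Platelet counts are taken at the start and end of the same five sessions. For coagulation tests and "platelet count on HD days, summary will be for pre- and post-HD and fold change".

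The Table 14.3.5.5 shell (SAP 10.3) has three columns per treatment group: pre-HD, post-HD and fold change. Its footnote, which covers every test in the table, reads "Fold change = Post-dialysis / Pre-dialysis". A programmer note adds that "for PT, INR and PT/INR, the pre-dialysis value will be the baseline value for that day", and that the change from baseline is to be that day's fold change.

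The list of tables in SAP 9.2 gives the same table a different title: "Clinical Laboratory Summary and Change from Baseline – Coagulation and Platelet Count (Safety Population"). The shell title leaves out the change from baseline. The shift tables in SAP 7.4 are for serum chemistry and hematology only.

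Protocol 14.3.1 plans descriptive statistics for quantitative safety data "as well as for the difference to baseline, when appropriate". Protocol 14.3.3, which covers pharmacodynamics, states: "Any values after a single dose of E-WE thrombin are regarded as post-baseline values".

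**The concern.** Coagulation tests are named in the primary safety outcome, which compares active treatment with pre-treatment and with placebo (Protocol 9.2, SAP 2.2). A Day 3 ratio of post-HD to pre-HD contains no pre-treatment value, so it cannot make the first of those comparisons. It describes what one dialysis session did to a patient who had already been dosed.

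The SAP handles its other safety measurements differently. Chemistry and hematology (7.4), vital signs (7.5) and ECG (7.7) all take baseline from before the dose. Coagulation, the laboratory domain closest to the drug's mechanism, is the exception. For PT and INR the shell goes further and calls the Day 3 pre-dialysis value a baseline. At stake is a Day 3 change column that could read as no change, or as a change in the wrong direction, while a drug effect was still present.

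**Working it through.** **Inputs.** The dose starts with the Day 1 HD session (Protocol 11.4.3). Pre-HD samples are taken within 1 hour before HD (Protocol Section 6, footnote g). A session lasts about 4 hours (Protocol 13.3). There are 12 active patients per dose level (Protocol 10.1). The documents state no Day 3 effect size, so the effect sizes below are assumptions.

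**1. Schedule check.** Coagulation: Day -8, five HD days × 2, and Follow-up = 1 + 10 + 1 = 12. Platelets: 5 × 2 = 10. Both agree with Protocol Table 3 (12, and up to 10).

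**2. Which denominators are predose.** On Days -7, -5, -2 and 1 the pre-HD sample precedes the dose. On Day 3, with sessions starting at the same clock time, it falls between 48 − 1 = 47 and 48 hours after dosing starts. HD days supply three post-dose samples: Day 1 post-HD, Day 3 pre-HD and Day 3 post-HD. Only the first is divided by a predose value.

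**3. Algebra.** Let B be the Day 1 pre-HD value, h the effect of a session on post/pre, and m1 and m2 the multiplicative drug effects before and after the Day 3 session. Assume that without drug the Day 3 pre-HD level would again be B.

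- Day 3 pre-HD = B × m1; Day 3 post-HD = B × h × m2
- Planned fold change = h × m2 / m1
- Ratio to Day 1 pre-HD = m1 (pre-HD) and h × m2 (post-HD)

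**4. Stable effect (m1 = m2).** The fold change equals h whatever the drug effect. With h = 1 it is 1.00 for m = 0.7, 0.8, 1.2, 1.5 and 1.8 alike, while the ratio to Day 1 pre-HD is 0.7, 0.8, 1.2, 1.5 and 1.8. With h = 1.05 and m = 0.8 the fold change is 1.05, while the ratios to Day 1 pre-HD are 0.80 and 0.84.

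**5. Fading effect.** If the excess decays with half-life T hours over the 4-hour session, m2 = 1 + (m1 − 1) × 0.5^(4/T). For m1 = 1.5, h = 1 and T = 4: m2 = 1 + 0.5 × 0.5 = 1.25, and the fold change is 1.25 / 1.5 = 0.83.

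| Assumed T (h) | Planned Day 3 fold change | Day 3 post-HD / Day 1 pre-HD |
|---|---|---|
| 4 | 0.83 | 1.25 |
| 12 | 0.93 | 1.40 |
| 24 | 0.96 | 1.44 |
| 48 | 0.98 | 1.47 |

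A prolongation would therefore show as a ratio below 1. Decreases mirror this: for m1 = 0.8 and the same half-lives, the fold change is 1.13, 1.05, 1.03 and 1.01, while the true post-HD ratio is 0.90, 0.84, 0.82 and 0.81.

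**6. What group summaries lose.** For n = 12, the standard error of a mean change is √(2(1 − r)/12) in SD units, where r is the within-patient correlation. An assumed r of 0.5 gives 0.29 and r = 0.9 gives 0.13. A reader who has only the two group means and SDs, and treats them as independent, has √(2/12) = 0.41.

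**The case against.** A reader might infer that any lasting drug effect cancels out and is hidden from the report. The documents do not support that. Cancellation is exact only for a stable proportional effect, and it touches one column. Table 14.3.5.5 also summarises pre-HD and post-HD levels for every HD day, by dose and pooled placebo, so a lasting shift would appear there against Day 1 pre-HD and against placebo. With complete pairs, the difference between two displayed means equals the mean within-patient difference. What is missing is its spread and the individual ratios. Pairs may also be incomplete, because SAP 7 summarises whatever data are available. Individual values are listed (Appendix 16.2.8.1.3) and out-of-range results are tabulated (Table 14.3.4.2). The listing's programmer note does not name aPTT, but SAP 7.4 includes it among the parameters to be listed.

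A reader might also infer that platelets have no change from a predose baseline. That is too strong. Platelet count is in the hematology panel (Protocol 13.2.7). SAP 7.4 takes hematology at the end of HD on Day 3 and gives each test a change from the last predose result and a shift table. Because SAP 7.4 also presents platelets with coagulation, it should say that they remain in the hematology tables.

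The conflict with the protocol is thin. The rule that values after dosing are post-baseline stands in the pharmacodynamic section, the safety section plans a difference to baseline only where appropriate, and the programmer note on a daily baseline names only PT, INR and PT/INR.

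On likely impact, Protocol 8.2.2.2 reports that in healthy subjects aPTT was back to baseline by 4 or 24 hours depending on dose, with no significant effect on PT, platelets or fibrinogen. That stands, but those were bolus doses. This trial adds a 4-hour infusion meant to sustain the effect (Protocol 8.3.2), and Protocol 8.4 says hemostatic safety in ESRD and chronic HD is not yet known.

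**Conclusion.** The point holds in a limited form. For aPTT, PT/INR, fibrinogen and TT, the one within-patient change planned for Day 3 does not measure change from pre-treatment. It returns only the session effect when a drug effect is stable, and it moves against the drug effect when that effect is fading. Day 1 is unaffected, and platelets are less affected provided they stay in the hematology tables.

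The numerical size rests on assumed effects and half-lives. The conclusion that the Day 3 ratio lacks a predose value rests only on the dosing and sampling schedule; the 47–48 hour figure assumes equal session start times. The likely impact is limited, because the first-in-human results give no sign of an effect lasting to Day 3 and the group summaries would show one. It is still worth correcting: whether an effect has gone by Day 3 in this population is a question for these samples, and the planned change column does not answer it.

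**What to change.** In SAP 7.4 and the Table 14.3.5.5 shell:

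- Define baseline for the coagulation tests and HD-day platelets as the last predose value (Day 1 pre-HD).
- Add the within-patient ratio or change from that baseline for Day 1 post-HD, Day 3 pre-HD and Day 3 post-HD, by treatment.
- Keep the same-day ratio, label it *HD effect (post/pre)*, and remove the wording that makes the pre-dialysis value that day's baseline.
- Reconcile the table title in SAP 9.2 with the shell title in SAP 10.3.
- Confirm that platelet count stays in the hematology change-from-baseline and shift tables.

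Comparing Day 3 post-HD with the patient's mean post-HD value over the run-in sessions would match for the dialysis effect, but is optional.

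The cost is SAP wording and extra columns in one table. All samples are already scheduled.

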7.5 Vital Signs

Vital signs tests (HR, BP, RR and T) will be assessed at Screening, Day -8 check-in, within one hour prior to start of HD on Days -7, -5, -2, 1 and 3 and 1 hour postdose on Day 1.

Vital sign results will be summarized by treatment and time point. Change from baseline will be summarized in a similar way. Baseline is defined as the result closest and prior to the dose on Day 1, which may include unscheduled results, whichever is later. Postdose unscheduled events will not be included in summaries.

7.6 Weight

Weight will be assessed at Screening, Day -8 check-in, at start and end of HD on Days -7, -5, -2, 1 and 3. Weight will be summarized by treatment and time point.

7.7 ECG

Safety ECGs (HR, PR, QRS, QT and Fridericia correction QTcF) will be assessed at Screening, Day -8 check-in, Hour 0.5 postdose Day 1 and end of HD on Day 3.

ECG parameters will be summarized by dose level, pooled placebo, and time point. Change from baseline will be summarized in a similar way. Baseline is defined as the result closest and prior to the dose from Day -8 check-in, which may include unscheduled results, whichever is later. Postdose unscheduled events will not be included in summaries.

The QTcF values that are > 450 ms and increase from baseline > 30 ms will be flagged in the data listings.

7.8 Concomitant Medications

All concomitant medications recorded during the study will be coded with the WHO Dictionary Version September 2018, B3 and listed.

7.9 Physical Examination

Full physical examinations will be performed at Screening, Day -8 check-in and end of HD on Day 3. Abbreviated physical examination will be performed at Hour 0.167 on Day 1 or at other times, at the PI's or designee's discretion. Abnormal findings will be reported as medical history or adverse events. All data found in the CRF will be listed.

7.10 Vascular Access Site Reaction

Vascular access site reaction will be assessed at predose and 4 hours post dose on Day 1 and at start and 20 minutes post HD on Day 3. Any new abnormal findings inconsistent with past skin injuries as expected in patient on chronic HD will be reported and summarized as AEs. All data collected on the CRF will be listed.

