- a For details on Procedures, refer to [Section 13](#).
- b Within 28 days prior to Day -8.
- c All patients who receive the study drug or matching placebo (including patients who terminate the study early) will return to the CRU on Day 14 (± 2 days) for coagulation tests, immunogenicity sample collection, and to determine if any AE has occurred since the last study visit.
- d Patients will be admitted to the CRU on Day -8, at the time indicated by the CRU, and will remain confined up to Day 3 or early termination.
- e During confinement to the CRU, patients will undergo HD 5 times: on Day -7, -5, -2, Day 1, and Day 3. For each patient, the HD will last approximately 4 hours as per patient standard schedule which will be the same throughout the study.
- f Symptom-driven physical examination may be performed at other times, at the PI's or designee's discretion.
- g To be performed within 1 hour prior to the start of HD.
- h To be performed at the end of HD.
- i The HD vascular access sites (AV fistula or AV graft puncture sites) are to be evaluated immediately after the end of HD and removal of the needles from the fistula or graft for bleeding cessation or other reactions.
- j Samples for serum chemistry will be obtained following a fast of at least 4 hours, however, in case of dropouts or rechecks, patients may not have fasted for 4 hours prior to the serum chemistry sample is taken.
- k For anuric patients, UA may not be performed.
- l Coagulation parameters include aPTT, PT/INR, fibrinogen, and TT.
- m A single dose of E-WE thrombin or matching placebo will be administered into the dialysis line according to the randomization schedule, upon initiation of the HD procedure. The dose will be administered as a bolus dose immediately followed by a continuous infusion over 4 hours. Hour 0 will correspond to the beginning of E-WE thrombin bolus administration.
- n The dialysate sample will be taken at 30 minutes and at 3 hours after the start of HD. The dialysate will be frozen and sent to Aronora.
- o To be performed when the dialyzer cartridge is removed and collected at the end of HD.
- p To be performed within approximately 20 minutes after completion of HD.

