A placebo arm is included in this study design in order to robustly demonstrate the safety and efficacy of E-WE thrombin while not placing the patients at unnecessary risk, as mentioned above. The primary endpoint in this study is safety, measured as the number or frequency/rate of AEs that occur during the comparable observation periods. A heparin-free inpatient HD observation period (from Day -8 to Day 1 prior to dosing) is included in the trial design to establish a baseline for the heparin-free procedure. Continuation of the heparin-free HD procedure during the subsequent trial period and inclusion of a placebo arm allows for the determination of whether an AE is drug-related or not and permits accurate assessment of the safety of the study drug. The addition of a placebo arm also removes potential bias from the interpretation of AEs by the PIs and from the reporting by the patients. The secondary endpoint for this study is efficacy of E-WE thrombin on HD which may be more clearly observed with a placebo control instead of an active control (e.g., heparin). While the placebo arm may be at the same risk of clotting within the dialysis circuit as during the pre-dosing period (Days -8 to 1), data cited above suggests that these patients will not be at higher risk for either thromboembolic or bleeding complications. Should clotting occur within the dialyzer cartridge during a HD session that results in dialyzer failure, the dialyzer cartridge will be replaced, and the patient will be closely monitored by

the PI. It is important to note that replacement of the dialyzer cartridge during HD is safe for the patient and a routine procedure in cases of dialyzer failure.

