9.2 Study Endpoints

Primary outcome measures:

- The safety and tolerability of E-WE thrombin following active treatment will be evaluated versus pre-treatment and placebo by number and severity of AEs (including HD vascular access site reactions), physical examinations, bleeding time from the HD vascular access sites, vital sign measurements, 12-lead ECGs, clinical laboratory tests, and coagulation tests.

Secondary outcome measures:

- PD of E-WE thrombin will be measured by APC-PCI and plasma APC-PCI will act as a surrogate marker for E-WE thrombin drug exposure.
- Efficacy of antithrombotic activity will be evaluated by thrombus accumulation within the dialyzer cartridge (evaluated by visual inspection) after E-WE thrombin active treatment versus pre-treatment and placebo.
- Efficiency of HD will be assessed using BUN levels before and after dialysis to determine urea removed by 4 hours of dialysis (Kt/V and URR) after E-WE thrombin active treatment versus pre-treatment and placebo.

Other outcome measures:

- Development of antibodies to E-WE thrombin or WT thrombin after drug exposure.

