2.2 Endpoints

Primary outcome measures:

- The safety and tolerability of E-WE thrombin following administration of the active treatment will be evaluated versus pre-treatment and placebo by number and severity of AEs (including HD vascular access site reactions), physical examinations, bleeding time from the HD vascular access sites, vital sign measurements, 12-lead ECGs, clinical laboratory tests, and coagulation tests.

Secondary outcome measures:

- Pharmacodynamics of E-WE thrombin will be measured by APC-PCI and plasma APC-PCI will act as a surrogate marker for E-WE thrombin drug exposure.
- Efficacy of antithrombotic activity will be evaluated by thrombus accumulation within the dialyzer cartridge (evaluated by visual inspection) after E-WE thrombin active treatment versus pre-treatment and placebo.
- Efficiency of HD will be assessed using BUN levels before and after dialysis to determine urea removed by 4 hours of dialysis (Kt/V and URR) after E-WE thrombin active treatment versus pre-treatment and placebo.

Other outcome measures:

- Development of antibodies to E-WE thrombin or WT thrombin after drug exposure.

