Appendix 16.2.8.4 Vascular Access Site Reaction Assessment (Safety Population)

Subject Number	Cohort/ Treatment	Study Day	Study Hour	Collection Date	Actual Time	Was a Reaction Observed?	If yes, Grade (1,2 or 3)
X	1/A	1	Predose	DDMMYYYY	HH:MM	XXX	X
			4 Hours postdose	DDMMYYYY	HH:MM	XXX	X
		3	Start of HD	DDMMYYYY	HH:MM	XX	
			20 min Post HD	DDMMYYYY	HH:MM	XXX	X

Note: Treatment: A = 0.5 µg/kg bolus dose of E-WE Thrombin followed by a 0.25 µg/kg/hour continuous infusion over 4 hours for a total dose of 1.5 µg/kg

B = 1.0 µg/kg bolus dose of E-WE Thrombin followed by a 0.5 µg/kg/hour continuous infusion over 4 hours for a total dose of 3.0 µg/kg

P = Placebo

HD = Hemodialysis

Program: /AXXXXX/ECR/sas_prg/stsas/lis_PROGRAMNAME.sas DDMMYYYY HH:MM

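### No structured, graded post-HD access-site assessment is scheduled before dosing, so the pre-treatment comparison named in the primary endpoint may be affected by unequal ascertainment

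*SAP*

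**What the plan says.** **Endpoint.** Protocol 9.2 evaluates safety after active treatment "versus pre-treatment and placebo by number and severity of AEs (including HD vascular access site reactions" and through several other measures. SAP 2.2 repeats this: "evaluated versus pre-treatment and placebo by number and severity of AEs (including HD vascular access site reactions". Protocol 8.3.1 describes the primary endpoint as "measured as the number or frequency/rate of AEs that occur during the comparable observation periods" and presents the heparin-free run-in as the source of the baseline.

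**Schedule.** SAP 7.10: "Vascular access site reaction will be assessed at predose and 4 hours post dose on Day 1". For the second session from dosing on, the same section sets two further assessments, "at start and 20 minutes post HD on Day 3". The vascular access row of the flow chart (Protocol 6) and the listing shell "Appendix 16.2.8.4 Vascular Access Site Reaction Assessment (Safety Population") show the same four time points and no others. The shell has two result fields: whether a reaction was observed, and its grade (1 to 3).

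**Other capture of reactions.** Flow chart footnote i, attached to the bleeding-time row on all five HD days, has the puncture sites "evaluated immediately after the end of HD and removal of the needles from the fistula or graft for bleeding cessation or other reactions". Protocol 13.2.5 makes new abnormal access-site findings AEs. Protocol 13.2.8.2 and 13.2.8.3 collect AEs from check-in, with one question per day during confinement and a severity rating for each event.

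**Analysis.** Protocol 14.3.1 plans a summary of access-site reactions by treatment and time of collection. SAP 7.10 summarizes them only as AEs and lists the form data. SAP 7.3 summarizes only treatment-emergent AEs. SAP 8 reports no departure from the protocol's analyses.

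**The concern.** A before/after comparison of event counts is informative only if events are looked for in the same way in both periods. From Day 1 the sites are examined on a schedule, with a yes/no answer and a grade against fixed thresholds for pain, tenderness, redness and swelling. Before dosing there is no such examination after needle removal, which is when a reaction to cannulation would be expected to show. The one pre-treatment form is filled in before the Day 1 session, so it can show only what remains from Day -2 or earlier.

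Bleeding time, coagulation, platelets, BUN and clotting grade are all recorded after HD on all five HD days. Access-site grading is the exception, although the endpoint names it for comparison with pre-treatment. With only 12 pooled placebo patients, the within-patient contrast carries some weight in this design. If mild reactions go unrecorded before dosing and are recorded afterwards, the drug could appear to cause reactions that belong to the procedure.

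**Working it through.** The plan gives no rate, power or error figure for access-site reactions, and Protocol 14.1 says the sample size had no statistical basis. There is no stated result to reproduce beyond the enrolment total: 2 × (12 + 6) = 36, that is 24 active and 12 placebo.

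**Step 1. Count the scheduled looks per patient.**

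| | Days -7, -5, -2 and Day 1 before dosing | From dosing on (Days 1 and 3) |
|---|---|---|
| Structured form, any time | 1 (Day 1 predose) | 3 |
| Structured form, after HD | 0 of 3 sessions | 2 of 2 sessions |
| Footnote i check after HD | 3 of 3 sessions | 2 of 2 sessions |
| AE reporting | yes, from check-in | yes |

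Over 36 patients, the post-HD form is planned on 0 of 3 × 36 = 108 occasions before dosing and on 2 × 36 = 72 of 72 from dosing on. This counts forms; it does not measure bias.

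**Step 2. Compare the two kinds of look.** Footnote i asks for a check right after needle removal and gives no scale. The form is completed within about 20 minutes of the end of HD and uses the scale in Protocol 13.2.5. Protocol 13.2.6, which describes the bleeding check, covers pressure and bleeding only. SAP Appendix 16.2.5.9.2 shows a field for time to hemostasis but none for reactions. Before dosing, a reaction is captured if someone notices it and reports it as an AE.

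**Step 3. Illustrate the effect of unequal capture with no drug effect.** Both inputs are assumptions, not in the documents:

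- p = true probability of a reaction per session, the same in both periods, with sessions independent
- s = share of reactions captured before dosing, relative to capture with the form

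Per-session ratio, after to before: p / (p × s) = 1/s.

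Patients with at least one detected reaction among the 24 active: before, 24 × [1 − (1 − p·s)³]; after, 24 × [1 − (1 − p)²].

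With p = 0.10, the after value is 24 × (1 − 0.90²) = 24 × 0.19 = 4.6. For s = 0.25, the before value is 24 × (1 − 0.975³) = 24 × 0.073 = 1.8.

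| s | Per-session ratio | Patients before (p = 0.10) | Patients after (p = 0.10) |
|---|---|---|---|
| 0.25 | 4.0 | 1.8 | 4.6 |
| 0.50 | 2.0 | 3.4 | 4.6 |
| 0.75 | 1.33 | 5.0 | 4.6 |
| 1.00 | 1.0 | 6.5 | 4.6 |

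At s = 0.25 the patient counts are 0.9 against 2.3 for p = 0.05, and 3.4 against 8.6 for p = 0.20.

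The last two rows show a second point. Because three sessions are set against two, per-patient counts are not comparable even with equal capture, so the contrast has to be made per session.

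**Step 4. Placebo contrast.** Both arms follow one schedule. With no drug effect, the expected proportion with a detected reaction after dosing is 1 − (1 − p)² in each arm (0.0975, 0.19 and 0.36 for p = 0.05, 0.10 and 0.20), a difference of 0.

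**The case against.** The strongest reply is that reactions are sought before dosing too. Footnote i has the sites checked for reactions after every session, AEs are recorded from check-in, and a new site finding is an AE. AE severity is rated on the same FDA toxicity scale that Protocol 13.2.5 uses for the form, so a reaction seen after HD on Day -7 should be reported and graded. This stands. A reader might infer from the schedule that no post-HD baseline exists, or that no reaction before dosing can carry a grade. The documents do not support that; what is missing is a scheduled, structured assessment.

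A reader might also infer that the before/after comparison is shown to be biased, or cannot be interpreted. That does not follow either. The result depends on s, which the documents do not give, and at s = 0.75 the per-patient excess has gone. Any bias would run against the drug.

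It can also be said that attribution rests on the randomized, double-blind placebo arm, and that this is one component of a descriptive endpoint. Both are true and limit the weight of the point. They do not remove it, because both documents name pre-treatment as a comparator.

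Finally, the SAP tabulates no before/after contrast for site reactions. That is a further gap rather than a defence, since Protocol 14.3.1 plans a summary by treatment and time.

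**Conclusion.** The point holds as a mismatch between endpoint and data collection. The form is scheduled after HD at 0 of 3 sessions before dosing and 2 of 2 from dosing on, and the pre-treatment baseline for access-site reactions rests on an unstructured check and AE reporting. The comparison with pre-treatment may therefore be affected by unequal ascertainment, toward more reactions after dosing and by an unknown amount. The ratios of 1.33 to 4.0 illustrate assumed capture shares of 75% down to 25%; they are not estimates. The placebo comparison is not affected.

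The change is worth making but is not critical: it concerns one contrast for one component of a multi-part safety endpoint with no formal test. The conclusion assumes that no reaction form is completed on Days -7, -5 and -2 beyond what the flow chart, SAP 7.10 and the listing shell show.

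**What to change.** - Complete the same reaction form (observed yes/no, grade) after HD on Days -7, -5 and -2, within the same time window as on Days 1 and 3. The inspection is already required by footnote i.
- Add those days to the flow chart row, SAP 7.10 and Appendix 16.2.8.4.
- Add a table of access-site reactions by treatment and time point, reported per session because three sessions before dosing are set against two from dosing on. This also supplies the summary that Protocol 14.3.1 plans and SAP 7.10 leaves out.
- If the added form is not feasible, state in the SAP that access-site reactions are interpreted against placebo only, and record this in SAP 8 as a change from the protocol.

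With equal capture (s = 1), the per-session ratio with no drug effect is 1.0 for any p. The cost is a small added site and CRF workload, at most 3 × 36 = 108 further forms, plus one table.
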